10.2 Collection of outcome data and follow-up assessments

Participants will receive communications from the SENTINEL study team to collect outcome data and undergo research specific visits.

Refer to Section 17.3 for full details of outcome data collection and follow-up assessments.

For those who consent to take part in the SENTINEL study. The following information will be recorded on a secure web-based form in the SENTINEL study database system (REDCap) by a member of the local study team to enable follow-up/contact:

• Participant details e.g. Name, Hospital number, address, NHS/CHI number, date of birth, telephone number, mobile number, email address, GP name and GP address.

The GP details are required to allow the central study team to send a letter to the participant's GP informing them of their SENTINEL participation after a transplantation procedure. The email address will enable a copy of the completed consent form to be sent to the participant or at their request a different individual for safekeeping. Depending upon participant preference the email /postal address and/or telephone may be utilised for follow up questionnaires, reminders/text messages and thank you letters. This information always be sent in an anonymised form without direct identifiers. Any confidential information that is sent will be marked confidential and will be encrypted and password protecrted.

After consent (Stage 1) baseline data and Health Related Quality of Life will be collected. Baseline HRQoL questionnaires will either be completed on paper or electronically on a tablet device/computer at the recruiting transplant centre. Patients will be sent HRQoL questionnaires again via e-mail or post (according to participant preference) at 3 months, and at 12 months post-randomisation. Questionnaires may also be completed during clinic visits at these time points if the participant has not already completed these when they come in for their visit.

On a suitable SENTINEL recipient / donor match that includes the offer of lungs and skin being found and flagged by NHSBT to the local SENTINEL Study Point of Contact, the potential recipient will be asked by the local team if they are still happy or not to participate in the study. A further consent is then taken and the participant is then randomised.

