15.5 Re-randomisation following non-transplant

Randomised patients (i.e. those that have consented to the study and been offered and accepted an organ) who do not receive transplantation will return to the waiting list and be re-randomised if they are offered lung and skin donation in the future. Patients will repeat stage 2 consent prior to randomisation and their HRQoL questionnaires will remain valid.

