17.3 Data Collection

Baseline data

Once Stage 1 consent has been obtained, baseline data collection can commence, including the baseline HRQoL questionnaires (SF-36, EQ-5D-5L and DAS-24). Where possible, baseline questionnaires will be completed electronically by the participant. Paper questionnaires may also be used where use of electronic means is not possible or suitable. Where paper-based questionnaires are used, data will be entered into the study database by the local site research team.

Once Stage 2 consent has been obtained (telephone or in person), further baseline data will be collected. This may be before or after randomisation depending on the time available between Stage 2 consent and the transplant taking place.

Completed at hospital by local study team member from medical notes or with participant prior to transplant

Sourced/collected by local study team	Direct patient report
 Date of baseline visit Participant demographics which will include: Date of birth Sex Height and weight (to calculate BMI) Ethnicity Reason for requiring lung transplant Co-morbidities Contact details of participant Participant's NHS/CHI number 	 Health-related quality of life* SF-36 (unmodified) EQ-5D-5L (unmodified) DAS-24 (unmodified)
Collected after transplant: Transplant outcome Date of transplant Skin flap transplant details to include: Location of transplanted flap Operating time/duration Reason for not receiving a transplant or not receiving the sentinel skin flap (if randomised to skin flap arm) Transplant type Organs transplanted Details of donor matching^ Donor age, sex and weight^ Cold ischaemia time (lung) Operating time/duration	

•	Details of induction and regular
	immunosuppression
•	Surgical complications
•	Bionsy results

Completed by dedicated skin flap retrieval and transplant team after transplant

Sourced/collected by local study team

- Details of skin flap retrieval which will include:
 - o Skin flap retrieval outcome
 - o Skin flap transplanted
 - o Reason for non-transplant
- Presence of an arterial line prior to skin flap retrieval.

Follow-up data

3 months post-transplantation

Sourced/collected by local study team	Direct patient report

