24.4 Description of Statistical Methods

Results will be reported in line with the CONSORT statement and relevant extensions (41)(42).

All outcomes will be summarised using descriptive statistics overall and, when collected for both arms, split by treatment groups. Binary and categorical data will be summarised by frequencies and percentages. Continuous data will be summarised by means and standard deviations (SDs), or median and inter-quartile range if data are skewed. Corresponding 95% confidence intervals will be presented where possible. Visual representation of outcomes will be considered and, where it will support interpretation, presented.

Analysis will be conducted using a complete case approach, no imputation methods for missing data are planned. Analysis of the primary and secondary outcomes will be done once the 12 month follow up has been reached by the last patient. Analyses of these outcomes will be pre-specified in a statistical analysis plan finalised prior to un-blinding of the data. Analysis of mechanistic outcomes, using sample data, will be done following completion of the primary and secondary outcomes.

An independent Data and Safety Monitoring Committee (DSMC) will meet early in the trial to agree its terms of references. They will review confidential interim analyses of accumulating data, including the interim analysis of the stop-go criteria and diagnostic accuracy.

It is anticipated that all statistical analysis will be undertaken using Stata (StataCorp LP, www.stata.com) or other well validated statistical software.

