24.6 Secondary outcomes

For diagnostic accuracy of the first test taken, proportions of observed true positives, true negatives, false positives and false negatives will be presented. Estimates of sensitivity, specificity, positive and negative predictive values will be generated, as well as the positive and negative likelihood ratios together with corresponding 95% confidence intervals, using the Wilson method. Diagnostic accuracy will be calculated for rejection events diagnosed by both methods (biopsy and clinical) for the entire trial period. A sensitivity analysis will include data for the first three months of patient follow up (to which point all suspected rejections are diagnosed using biopsy). Skin flap rejection events, by severity, will be summarised descriptively. Time to first skin flap rejection, transplanted lung and patient survival will be analysed following the methods used for the primary outcome. Competing risks will be considered if the number of deaths not related to the transplanted organ is sufficiently high to warrant such analyses. Transplant lung function (vital capacity, forced expiratory volume) will be analysed using mixed-effects linear regression models, including treatment, and adjusted for centre as a random effect. Development of de-novo specific antibodies, development of graft versus host disease, and evidence of chronic rejection, will be analysed using a mixed-effects logistic regression model, including treatment, and adjusted for centre as a random effect. Safety events (AEs, SAEs, complications), immunosuppressive levels (and requirements) and immunological markers will be summarised descriptively. HRQoL outcomes will be analysed using mixed-effects linear regression model, including treatment and adjusted centre and patient as random effects. Supplementary analyses of HRQoL will also use the area under the curve statistics.

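### The HRQoL model in Protocol 24.6 makes no use of the pre-randomisation score as a covariate and leaves open whether that score is a response

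*Protocol*

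**What the plan says.** Section 24.6 gives one main model for quality of life: "HRQoL outcomes will be analysed using mixed-effects linear regression model, including treatment and adjusted centre and patient as random effects". The next sentence adds a second analysis: "Supplementary analyses of HRQoL will also use the area under the curve statistics". Neither sentence names the baseline score.

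The baseline score exists for a clear purpose. Section 10.2: "After consent (Stage 1) baseline data and Health Related Quality of Life will be collected". Section 17.3 says that once Stage 1 consent is in place "baseline data collection can commence, including the baseline HRQoL questionnaires (SF-36, EQ-5D-5L and DAS-24") may begin, and Table 3 places the questionnaires in the waiting-list column. The score therefore precedes randomisation. If a participant is re-randomised after a transplant that did not go ahead, section 15.5 says "their HRQoL questionnaires will remain valid".

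Follow-up scores come twice. Section 10.2: "Patients will be sent HRQoL questionnaires again via e-mail or post (according to participant preference) at 3 months, and at 12 months post-randomisation".

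The secondary outcome table in section 9.3 (objective 4) gives baseline, 3 months and 12 months as the time points of evaluation. Nowhere does the protocol say whether the baseline value is a response or a covariate. Section 24.4 adds: "Analysis will be conducted using a complete case approach, no imputation methods for missing data are planned".

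**The concern.** A score taken before randomisation has an expected difference of zero between the arms. It can be used in an analysis in two main ways: as a covariate, where it improves precision, or as a constrained first response. The stated model does neither. It has one treatment coefficient and no term through which baseline enters.

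That leaves two readings of the same sentence:

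- Baseline is one of three repeated responses. The single coefficient then mixes a difference that is zero by design with the two differences of interest.
- Only the 3- and 12-month scores are responses. The coefficient is then a fair average of the two follow-up effects, but information already collected is not used.

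Objective 4 asks whether being able to check the graft, or having it visible, changes quality of life in either direction. A diluted or needlessly imprecise estimate could obscure a benefit or a harm. The two readings also estimate different quantities, so a reader of the protocol cannot tell which effect will be reported.

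**Working it through.** **Inputs from the protocol.** Model terms: 24.6. Occasions: baseline, 3 and 12 months (9.3, 10.2). Allocation 1:1 (15.3). Analysable participants: 128, or 64 per arm (24.2).

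**The plan's own figure.** No SD, effect size or power is given for HRQoL. The 64 per arm comes from the primary outcome, 80% against 53.33% with 90% power at two-sided 5%:

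n = [1.96·√(2·0.6667·0.3333) + 1.2816·√(0.80·0.20 + 0.5333·0.4667)]² / 0.2667² = (1.3066 + 0.8195)² / 0.0711 = 63.6, so 64 per arm and 128 in total. With 15% loss, 64/0.85 = 75.3, so 76 per arm and 152 in total. The protocol's figures reproduce.

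**Assumptions, not in the protocol.** Scores scaled to SD 1; random-intercept structure with correlation ρ between any two occasions, 0.3 to 0.7; the same effect d at 3 and 12 months; complete data.

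**Reading 1: baseline is a response.** With balanced data the treatment coefficient is the difference in participant means over three occasions:

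(0 + d + d)/3 = 0.67d.

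This factor does not depend on ρ or on sample size. In 150 simulated trials (d = 0.5, ρ = 0.5, centre fitted as fixed for simplicity) the mean estimate was 0.328 against a true 0.5. Adding a visit term while keeping baseline as a response left it at 0.328.

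**Reading 2: only follow-up scores are responses.** The estimate is unbiased. Per-participant variance of the contrast:

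- without baseline: (1+ρ)/2
- with baseline as covariate: (1+ρ)/2 − ρ²

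| ρ | without | with | ratio | effective sample lost |
|---|---|---|---|---|
| 0.3 | 0.65 | 0.56 | 1.16 | 14% |
| 0.5 | 0.75 | 0.50 | 1.50 | 33% |
| 0.7 | 0.85 | 0.36 | 2.36 | 58% |

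In the same simulation the mean estimate was 0.491 both without and with baseline (plus visit), and the mean standard error fell from 0.155 to 0.127. A constrained-baseline model gave 0.489 and 0.125.

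**A weaker baseline correlation.** The baseline is taken on the waiting list, may be old by the time of transplant, and has the transplant between it and follow-up. Let follow-up scores correlate at 0.5 with each other but at only 0.2 to 0.3 with baseline. The variance reduction is then 0.2²/0.75 = 5% to 0.3²/0.75 = 12%.

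**Illustrative power.** With d = 0.5 SD, ρ = 0.5 and 64 per arm, closed-form power is 64% under reading 1, 90% under reading 2 and 98% with baseline adjustment. These depend on the assumed effect and correlation; the protocol makes no power claim for HRQoL.

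**The case against.** The strongest reply is that section 24 is a summary. Section 24.1 leaves full detail to the SAP, which is not among the documents reviewed; the word for the model terms is 'including', which does not exclude others; and the lung-function and logistic models in the same section use a similarly short formula. Covariates and visit terms are routine SAP content. This stands as far as it goes: the point is not proof of what the final analysis will be. But the protocol does write down a model for an outcome whose baseline is deliberately collected, and that model makes no stated use of it. The area-under-the-curve analysis names no baseline adjustment either.

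A reader might infer more than the text supports:

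- That the stated model is biased. It is biased only if baseline is entered as a response, and no sentence says so. Section 9.3 makes that reading possible. The participant random effect does not imply it, because two follow-up scores per participant already call for one.
- That the missing visit term causes the dilution. It does not; the simulated estimate was the same with and without it.
- That scores are known to change sharply across transplantation. The protocol does not say so, and the point does not need it.
- That 12 months must be the main time point. An average effect over 3 and 12 months is a legitimate target, and the protocol ranks neither visit.

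It is also fair to say that dilution does not create false positive findings, and that the gain from adjustment may be modest if the waiting-list score is a poor predictor.

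**Conclusion.** The point holds as a recommended improvement to a secondary analysis. Section 24.6 does not use the pre-randomisation score as a covariate and does not settle its role.

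- If baseline is a response, the estimate targets about two thirds of the effect. This rests on complete data and equal effects at 3 and 12 months.
- If it is not, the estimate is unbiased, with variance about 1.2 to 2.4 times that of the adjusted model for a common correlation of 0.3 to 0.7. The cost is smaller, a 5% to 12% variance reduction forgone, if baseline correlates at only 0.2 to 0.3 with follow-up scores that correlate at 0.5 with each other.

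The documents do not support calling the planned estimate biased outright. The primary analysis and the 128/152 sample size are untouched.

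**What to change.** In section 24.6, state that the 3- and 12-month scores are the responses, and add the baseline score and visit as fixed effects, keeping treatment and the participant and centre random effects. A constrained-baseline model, with time and post-baseline treatment terms, serves the same aim. It also keeps participants with no baseline score, whom covariate adjustment under the complete-case approach of 24.4 would drop.

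Separate 3- and 12-month estimates through a treatment-by-visit term are optional, and the choice of a headline time point is for the sponsor. The cost is a sentence or two in 24.6, carried into the SAP before it is finalised. No new data, visits or participants are needed.

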24.7 Mechanistic outcomes

Mechanistic outcomes will be summarised using descriptive statistics overall and, when collected for both arms, split by treatment groups. Binary and categorical data will be summarised by frequencies and percentages. Continuous data will be summarised by means and standard deviations (SDs), or median and inter-quartile range if data are skewed. Corresponding 95% confidence intervals (CIs) to support simple group comparisons will be presented where possible. Visual representation of outcomes will be considered and, where it will support interpretation, presented.

24.8 Additional analyses

A supplementary analysis, using the approaches for the primary outcome, will be run using a composite outcome of rejection free survival, whereby lung rejection (ISHLT A grade 1 or higher), graft failures (biopsy BANFF grade \geq 1) and death are counted as events. As participants can have recurrent lung or skin rejection events, an exploratory analysis of the ordered multiple events will be undertaken using the Prentice, Williams and Peterson total time models (44). Visual representation of recurring events will also be presented.

24.9 Inclusion in analysis

The principle of intention-to treat (ITT), as far as practically possible will be the main strategy for the primary outcome and all secondary outcomes (except for Secondary Outcome 2d). ITT will analyse all randomised and transplanted patients, in the group to which they were allocated and for whom the outcomes of interest have been

observed/measured. To check the robustness of analysis under ITT, a secondary sensitivity per-protocol analysis, which will mirror the ITT population but exclude participates defined with a major protocol deviation, will be conducted. Secondary outcome 2d (safety events) will be analysed according to the safety population, which will include all participants who receive a transplant, where groups are defined according to whether or not they received a skin transplant.

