16.3 Management of skin retrieval

Not all lung donor families will agree to the donation of a skin flap as well. In order to avoid waste of retrieved, under-utilised skin flaps, the availability of both lung and skin donation must be confirmed prior to the randomisation. If the patient is randomised to lung only, the skin flap will not be retrieved. If the patient is randomised to lung and skin then both organs will be retrieved.

Around 50% of the time, the offer of the lung transplant is rejected by the transplant team as the lung is unfit for transplant. This decision could possibly be made as late as after randomisation has been performed and retrieval has already commenced. If skin flap retrieval has commenced prior to the decision not to proceed with lung retrieval and transplantation then the skin flap will be aesthetically sutured in place on the donor forearm and dressed. Obviously, the transplant and intervention cannot occur and the patient will return to the transplant waiting list. The patient will not retain their randomisation, as the next offer they receive may not include the offer of skin. They will need to be newly randomised next time, but only if their next offer has also agreed to skin flap donation. If the decision is made at the recipient hospital, then both lung and skin flap will follow NHSBT policy and either be offered for research (if the donor family had consented for this) or discarded.

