16.7 Sentinel skin flap retrieval

If a suitable donor, with consent obtained for both lung and skin donation is matched with a patient, their local participating site will be informed (in accordance with NHSBT procedures). The dedicated retrieval team will be contacted by the participating site to ensure availability for skin retrieval, as there may be situations where transplantation procedures are already underway elsewhere and retrieval of the skin flap is not possible. If the patient confirms their consent to take part in the study, they will be randomised. If they are randomised to receive a SSF, the dedicated retrieval team will be placed on standby to travel to the donor hospital to retrieve the SSF alongside the usual lung retrieval team.

If skin flap retrieval is not possible or viable then lung retrieval and transplantation will proceed as planned without skin flap transplantation.

Where a skin flap is retrieved and not transplanted, the NHSBT will be informed and the skin flap will be discarded or used in other research approved by NHSBT provided the family has consented for such use. The study database will record that the skin flap was retrieved and not used. Skin flaps not used for the purpose of this study will be tracked and documented within NHSBT systems to ensure that they are handled and managed appropriately and in accordance with relevant approvals.

In the unlikely event that two donations are approved at the same time, and the skin flap retrieval team are not available to retrieve both SSFs, then the donation logistically/geographically nearest to the retrieval team would take priority; and only that recipient randomised. If that recipient randomises to lung only then the second recipient may be randomised.

Rarely, a skin flap may be required for both a lung transplant, as part of this study, and a intestinal transplant, as part of another study. In this instance, the SSF will be split in two for each recipient or prioritised for the intestinal transplant.

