17.8 Participants that do not proceed to transplant

Participants who consent to be included in the study may not proceed to transplantation during the study period as:

- 1) they may not receive an offer of an organ;
- 2) may become too unwell or die;
- 3) may recover and no longer need transplantation.

17.9 Participants that are offered a transplant where skin has not been agreed to be also donated

Participants who consent to be included in the study may proceed to transplantation but not be randomised. If an organ is only offered for donation without skin – a matched individual will be offered the organ and if they take the transplant offer up – and it proceeds this will end their participation in the study. A thank you letter will be sent to the individual at this point.

17.10 Participants that are offered a transplant where skin is available and to which they are randomised to an SSF with their transplant but they do not receive the SSF but they still receive the lungs

Participants who consent and are randomised may not receive their allocation as the transplant fails to proceed as the lung donation is found to be inadequate for transplantation, or the skin flap is found inadequate for transplantation.

If the lung is not transplanted these participants will return to the lung transplant waiting list and will not be replaced.

If the lung is transplanted but the skin flap is not transplanted, these patients will cross over to the lung only arm of the trial.

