19.4 Surgical complications

The following treatment-related complications will be collected on the peri- and postoperative complications case report forms (CRFs) and should not be reported separately on a SAE form unless the complication is (in the opinion of the site investigator) considered more severe in nature than might be expected, or unexpected, for the particular intervention received by the participant.

Peri-operative complications (events occurring intraoperatively, during the immediate post-operative period, or in the first 14 days post-procedure):

Skin Flap:

- Bleeding/Haematoma
- Wound dehiscence
- Infection (spreading wound inflammation, purulent discharge requiring additional antibiotics)
- Arterial supply problem to the flap
- Venous supply problem to the flap
- Vascular supply deficiency
- Nerve supply to hand (numbness, paraesthesia, weakness, paralysis, palsy, stiffness, carpal tunnel syndrome)
- Delayed wound healing
- Flap necrosis: partial %/total

Lung Transplant:

- Pneumothorax
- Haemothorax
- Bleeding/Haematoma
- Wound dehiscence
- Wound Infection (spreading wound inflammation, purulent discharge requiring additional antibiotics)
- Empyema

- Vascular supply problem to the lung transplant
- Delayed wound healing
- Air leaks
- Bronchial anastamotic leak
- Bronchial stenosis
- Bronchial malacia
- Infection- cmv/other respiratory virus/aspergillus/mycobacterial/other
- Cryptogenic organising pneumonia
- Pulmonary embolism
- Pulmonary infarction

Post-Operative: Events occurring at any time during follow-up period likely related to a study intervention: (3 - 12 months) *from 2 weeks.

Skin Flap:

- Nerve supply to hand (numbness, paraesthesia, weakness, paralysis, palsy, stiffness, Carpal tunnel syndrome)*
- Infection (spreading wound inflammation, purulent discharge requiring additional antibiotics)*
- Arterial supply problem to the flap*
- Venous supply problem to the flap*
- Flap necrosis*
- Vascular supply deficiency
- Pain
- Tendon dysfunction

Lung Transplant:

- Bronchial dehiscence*
- Bronchial stenosis
- Bronchial malacia
- Infection- cmv/other respiratory virus/aspergillus/mycobacterial/other
- Cryptogenic organising pneumonia
- Pulmonary embolism
- Pulmonary infarction
- PTLD (post transplant lymphoproliferative disorder)
- GVHD (graft versus host disease)
- Chronic rejection
- Upper lobe fibrosis
- Post trans-bronchial biopsy related complications
- Bronchogenic carcinoma

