24.5 Primary outcome

The primary outcome of the study is absolute difference in rejection rates (clinical or biopsy) at 12 months post randomisation. The absolute risk difference, and corresponding 95% CIs, will be obtained from a mixed-effects Cox proportional hazards models, including treatment and adjusted for centre as a random effect, analysing time to first lung rejection (43). If the proportional hazards assumption is not met, alternative parametric methods will be considered. The treatment groups will also be compared using Kaplan-Meier curves and log rank tests. Events, by severity, will be summarised descriptively. Sensitivity analyses for the primary outcome will include alternative definitions of the primary endpoint, including lung rejections of ISHLT grade 2 or higher, and ISHLT grade 3 or higher. The primary analysis will

be repeated for the per-protocol population, excluding participants with major deviations from the study protocol.

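### Grouping surgical complications (2d) by flap received counts a flap operation that is started and then abandoned as lung only

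*Protocol*

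**What the plan says.** Protocol 24.9 takes outcome 2d out of the intention-to-treat strategy and assigns it to a safety population, "which will include all participants who receive a transplant", "where groups are defined according to whether or not they received a skin transplant".

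Two other sections foresee flap-allocated participants who get the lung but no flap. Section 16.7: "If skin flap retrieval is not possible or viable then lung retrieval and transplantation will proceed as planned without skin flap transplantation". Section 17.10, on participants whose lung is transplanted but whose flap is not: "these patients will cross over to the lung only arm of the trial". For the other arm, section 16.3 says: "If the patient is randomised to lung only, the skin flap will not be retrieved".

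Section 9.3 marks 2d as assessed in both arms. The flap complications listed in 19.4 include bleeding, infection, arterial and venous problems, and "Nerve supply to hand (numbness, paraesthesia, weakness, paralysis, palsy, stiffness, carpal tunnel syndrome". Section 19.1 starts safety reporting when the allocated treatment commences. Section 24.6 plans descriptive summaries only for complications.

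Section 17.3 collects "Reason for not receiving a transplant or not receiving the sentinel skin flap (if randomised to skin flap arm", the site of the transplanted flap, operating time and surgical complications. It lists no item for whether an incision was made at the recipient site.

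**The concern.** Outcome 2d is where the harm of the added arm operation should show, and that harm comes from operating, not from leaving theatre with a flap in place. If the recipient's arm is opened and the flap is then given up, the participant has had the exposure but not the flap. Under the rule in 24.9 that person, with any nerve, bleeding or wound problem, joins the recipients who had no arm surgery, and the flap group keeps only completed flaps.

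This matters because the safety of the flap is one of the trial's stated aims (9.1). Under 19.3 and 19.4 the listed complications stay off the SAE form unless they are unexpected or unusually severe, so the 2d summary is the main place they appear. With descriptive reporting only, nothing later in the analysis would correct a misplaced case.

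**Working it through.** **1. Reading the sections together.** Take each way in which a flap-allocated, transplanted participant can fare:

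- Flap lost at the donor, in transit, or for want of a team (16.7, 17.10), before the recipient's arm is touched: no flap received, no arm surgery. Counting this person as lung only misplaces no surgical harm.
- Flap inset, then thrombosed, necrotic or removed (16.12, 19.4): a flap was received. The participant and the harm stay in the flap group.
- Flap surgery started in the recipient, flap then not transplanted: no flap received, so lung only under 24.9 and 17.10. Harm from the attempt falls in the comparator, although 19.1 places it within the reporting period.

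Only the third route is a problem. The reverse move cannot occur, because no flap is retrieved for a lung-only participant (16.3).

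**2. The plan's own figure, needed for the denominator.** With 80% v 53.33%, two-sided 5%, 90% power and pooled variance, the mean proportion is 0.6667:

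n = (1.96 × √(2 × 0.6667 × 0.3333) + 1.2816 × √(0.16 + 0.2489))² / 0.2667² = (1.3067 + 0.8195)² / 0.0711 = 63.6, so 64 per arm and 128 in all. Then 64 / 0.85 = 75.3, so 76 per arm and 152 in all. This reproduces 24.2. Nothing in the present point changes it.

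**3. Illustration on assumed inputs.** The protocol gives no frequency of abandoned insets and no complication rate for them. Assume:

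- 76 transplanted per arm (24.2);
- flap-site complications only, with rate r = 20% after a completed flap and 0% without arm surgery;
- x attempts abandoned after recipient incision, each with complication risk q;
- no other flap-arm participant goes without a flap, so grouping by attempt and by allocation coincide.

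As received: flap group r; lung-only group xq / (76 + x); difference r − xq / (76 + x).

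By attempt or allocation: flap group [(76 − x)r + xq] / 76; lung-only group 0.

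For x = 4 and q = 50%: as received, 20% − 2/80 = 20% − 2.5% = 17.5 points. By attempt, (72 × 0.2 + 2) / 76 = 16.4 / 76 = 21.6 points.

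| x | q | Lung-only rate, as received | Difference, as received | Difference, by attempt |
|---|---|---|---|---|
| 2 | 25% | 0.6% | 19.4 | 20.1 |
| 4 | 25% | 1.3% | 18.8 | 20.3 |
| 4 | 50% | 2.5% | 17.5 | 21.6 |
| 8 | 50% | 4.8% | 15.2 | 23.2 |
| 12 | 100% | 13.6% | 6.4 | 32.6 |

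**4. When the difference is understated.** Setting the two differences equal gives q = r(76 + x) / (152 + x). For r = 20% and x = 4 this is 0.2 × 80 / 156 = 10.3%. Above that, the as-received grouping shows too small a difference. Below it, the flap group's rate is higher for losing low-risk attempts, and this offsets the misplaced events. Any harm from an abandoned attempt is still in the wrong column.

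**The case against.** The strongest reply is that no section describes an inset begun and then abandoned. The routes to non-receipt in 16.7 and 17.10 are mainly donor-side or logistical, and 16.5 has site and anatomy settled with the patient before surgery. Grouping safety data by treatment received is conventional. Because 19.4 lists flap and lung complications separately, a hand-nerve event in a lung-only recipient would stand out, and the reason for non-receipt is recorded. Much of this stands: the affected group may be very small, and an attentive reader of an itemised table could spot the case. It does not rescue the rule, which still gives a definite and wrong answer for that case; any total or percentage would carry the error.

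A reader might infer two stronger things.

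- **That the sickest flap-arm participants leave the flap group, tilting the whole complication comparison.** The documents do not show that non-recipients are sicker. If they carry average risk, moving them creates no difference in complications unrelated to the arm operation.
- **That the per-protocol set drops only failures from the flap arm.** Sections 24.5 and 24.9 word that exclusion without naming an arm, "excluding participants with major deviations from the study protocol", and neither classes flap non-receipt as a major deviation. Section 16.7 provides for it, 17.10 calls it a crossover, and 29.7 defines a deviation as a departure from the protocol. What counts as major is commonly left to the SAP. Only if non-receipt were so classed would that exclusion be confined to one arm.

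**Conclusion.** The point holds in a narrow form. The stated rule for 2d puts harm from a flap operation started and then abandoned into the lung-only group, and no opposite error can balance it. Flaps lost before recipient surgery and flaps that fail after inset are unaffected, as are the primary analysis and the sample size.

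The size is unknown and may be small. The figures above rest entirely on assumed complication rates and assumed numbers of abandoned attempts, and the upper rows are deliberately extreme. The understatement of the flap's risk also assumes that abandoned attempts carry more than about half the complication risk of completed flaps. The change is worth making because it is cheap and replaces a rule that misplaces harm, not because a large bias has been shown.

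**What to change.** In 24.9, define the flap group for 2d as participants in whom flap surgery was started in the recipient (incision at the forearm or other recipient site), whether or not the flap was completed. The remaining transplanted participants form the comparison group. Also tabulate 2d by allocated arm among transplanted participants. Flaps lost before recipient surgery count as no attempt in the first table and stay with their allocated arm in the second.

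The cost is one sentence, one extra table and possibly one CRF tick-box for recipient incision, since the data list in 17.3 gives the reason for non-receipt but no such item. A complier-average estimate of the primary outcome beside the per-protocol analysis is optional and is not needed to settle this point.
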